7.4.4 Cohort F

Disease control (DC)

DC as assessed by investigators is defined as a best overall response of CR or PR or SD and will be analysed. Descriptive statistics including number of treated patients, number of patients with objective response as best overall response and the corresponding percentages will be presented and evaluated.

7.5 SECONDARY ENDPOINTS

7.5.1 Key secondary endpoints

This section is not applicable as no key secondary endpoint has been specified in the protocol.

7.5.2 Other secondary endpoints

7.5.2.1 Cohorts A, B, C and D

This section is not applicable as no secondary endpoint has been specified in the protocol.

7.5.2.2 Cohorts E and F, D1 and D2

Disease control (Cohorts E, D1 and D2 only)

Disease control (DC) is defined as best overall response of complete response (CR) or partial response (PR) or stable disease (SD) (defined in [Section 5.2.2.2](#)). Only descriptive statistics are planned for this section of the report.

Time to OR

For patients with objective response, time to objective response will be shown on patient level. A set of summary statistics for time to objective response on cohort level will also be produced.

Duration of OR

KM estimates will be calculated for each treatment group to provide estimates of the median, 25th and 75th percentiles and their corresponding 95% CIs.

Duration of DC

Duration of DC will be analysed similarly to Duration of OR, see above.

Progression free survival

[figure not shown]
Kaplan-Meier estimates and 95% CIs (based on Greenwood's method) will be calculated. Furthermore progression free survival times on patient level will be shown and if applicable descriptive statistics including, but not limited to, the lower quartile (P25), Median and the upper quartile (P75) will be computed.

Objective response (Cohorts F, D1 and D2 only)

[figure not shown]
OR as assessed by investigators is defined as a best overall response of CR or PR and will be analysed. Descriptive statistics including number of treated patients, number of patients with

Proprietary confidential information © 2021 Boehringer Ingelheim International GmbH or one or more of its affiliated companies

objective response as best overall response and the corresponding percentages will be presented and evaluated.

Proprietary confidential information © 2021 Boehringer Ingelheim International GmbH or one or more of its affiliated companies

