 - age $<$ 60 years and amenorrheic (in the absence of tamoxifen, toremifene, ovarian suppression, or chemotherapy) for at least 12 months; and follicle-stimulating hormone (FSH) and estradiol within the postmenopausal range as per institutional reference ranges.
 - Postmenopausal status due to radiation-induced ovarian suppression must be confirmed by FSH and estradiol level in the postmenopausal range.
6. Histologically or cytologically proven diagnosis of breast cancer with evidence of locally advanced disease not amenable to curative resection or metastatic disease
7. HR+ (local lab results at screening or, if not available, at the time of diagnosis)
To fulfil the requirement of HR+ disease, the primary tumour or metastatic lesion of the breast cancer must express at least one of the hormone receptors (estrogen receptor [ER] or progesterone receptor [PgR]) by immunohistochemistry (IHC). Estrogen receptor and PgR assays are considered positive if there are at least 1% positive tumour nuclei in the sample as defined in the relevant American Society of Clinical Oncology (ASCO)/College of American Pathologists (CAP) Guidelines (Hammond et al. 2010).
8. HER2 negative (local lab results at screening or, if not available, at the time of diagnosis) as defined by the most recent American Society of Clinical Oncology (ASCO)/College of American Pathologists (CAP) Guidelines (Hammond et al. 2010).
9. Have a negative serum pregnancy test at baseline (within 14 days prior to randomization) and agree to use medically approved precautions to prevent pregnancy during the study and for 3 weeks following the last dose of abemaciclib and for at least 6 months after last dose of xentuzumab if postmenopausal status is due to ovarian suppression with a GnRH agonist.
10. Have either measurable disease or non-measurable bone only disease. Measurable and nonmeasurable diseases are defined according to the Response Evaluation Criteria in Solid Tumors (RECIST Version 1.1 [v1.1]. Nonmeasurable bone only disease may include any of the following: blastic bone lesions, lytic bone lesions without a measurable soft tissue component, or mixed lytic-blastic bone lesions without a measurable soft tissue component.

Cohort D1 and D2 only:

11. Patients must fulfil 1 of the following criteria:
 - a. Relapsed with radiologic evidence of progression while receiving neoadjuvant or adjuvant endocrine therapy, with no subsequent endocrine therapy received following progression.

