7.3 PLANNED ANALYSES

No per protocol set will be used in the analysis. However, important protocol violations will be summarised. The TSAP will specify the important protocol violations in detail.

For the determination of the MTD, only MTD evaluable patients will be considered. For the analysis of primary and secondary endpoints of the expansion parts and further endpoints of dose finding and expansion parts, all patients in the treated set (i.e. patients treated with at least one dose of any trial medication, including hormonal therapy) will be included in the analysis. Any other analysis sets will be defined in the TSAP.

The analysis of the primary endpoint of the dose finding cohorts (cohorts A, B, C and D (dose finding) respectively) will be conducted when “last-patient-last-visit-primary-endpoint-dose-finding” has been reached (see [Section 8.6](#)).

Primary analysis of expansion cohorts (cohort E, F, D1 and D2) might be done before the end of the study. The further details will be described in TSAP.

The results of each dose finding cohorts (A, B, C, and D (dose finding)) and each expansion cohorts (E, F, D1 and D2) will be analysed separately.

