5.1.2 Cohort E

The primary endpoint for the expansion part cohort E is objective response (OR).

Objective response (OR)

OR is defined as best overall response of complete response (CR) or partial response (PR), where best overall response is determined according to Response Evaluation Criteria In Solid Tumours (RECIST) version 1.1 from date of first treatment administration until the earliest of disease progression, death or last evaluable tumour assessment before start of subsequent anti-cancer therapy.

Best overall response

An adequate RECIST tumour assessment includes an assessment of target lesions (only for patients with measurable disease at baseline), as well as radiological tests to evaluate non-target lesions if any and to search for new lesions. In case no RECIST tumour evaluation has been performed, the assessment will be set to missing.

Best overall response is calculated based on the “overall” visit response from each assessment. Best overall response represents the best response a patient has had during his/her time in the study until progression, last evaluable assessment in the absence of progression or the start of subsequent anti-cancer therapy. For patients whose progression event is death, best overall response will be calculated based on data until the last evaluable RECIST assessment prior to death. (note that no confirmation is required for best overall response)

The following categories of best overall response will be derived:

- Complete response (CR)
- Partial response (PR) – possible only for patients with measurable disease at baseline
- Stable disease (SD) – possible only for patients with measurable disease at baseline

Proprietary confidential information © 2021 Boehringer Ingelheim International GmbH or one or more of its affiliated companies

- Subcategory “SD \geq Week 24” for breast cancer and “SD \geq 6 weeks” for NSCLC: calculated from randomization/treatment start until the earliest of disease progression, death or last evaluable tumour assessment before start of subsequent anti-cancer therapy. Here SD \geq Week 24 includes SD \geq 161 days taking into account allowable CTP window.
- Non-CR/Non-PD – possible only for patients with non-measurable disease at baseline

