6.3 PATIENTS SETS ANALYSED

The following analysis sets will be defined for this trial:

- Enrolled set (ENR)

This patient set includes all patients with informed consent given. The enrolled set will be used for patient disposition tables.

- Treated set (TS)

This patient set includes all patients who are documented to have received and taken at least one dose of any study medication during the treatment cycles (including run-in period).

The TS will be used for all planned safety and efficacy analyses.

- MTD Set (MS)

The MTD set defines the set of patients in the dose-finding cohorts (cohorts A,B,C and D) of the trial that are fully evaluable for determination of the MTD in the first treatment course. The MTD set will be used for some safety analyses for dose-finding cohorts, this is specified in the technical TSAP.

[figure not shown]
Patients in the TS who were replaced within the MTD period in the dose-finding cohorts (cohorts A,B,C and D) of the trial will be excluded from the determination of the MTD. Patients in the TS who entered in an expansion cohorts will be also excluded from the determination of the MTD. Replacement of patients in the dose-finding cohorts of the study is defined in Section 3.3.5 of the CTP. The final list of replaced patients is supplied by the Clinical Trial Leader (CTL) no later than the last report planning meeting before the database lock for the safety analysis.

- Pharmacokinetic set (PKS)

Proprietary confidential information © 2021 Boehringer Ingelheim International GmbH or one or more of its affiliated companies

This patient set includes all patients in the treated set who have at least one valid drug plasma concentration available. The decision whether a concentration is considered valid or not will in general be made at the RPM before Database Lock (DBL) or URPM and documented within the respective meeting minutes. Values to be excluded from analyses identified during analysis would be documented within the respective QC forms. The PKS will be used for the PK analyses of the trial.

No per protocol population will be used for analyses.

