7 PLANNED ANALYSES

The labelling and display format of statistical parameters will follow BI standards (9).

Unless otherwise specified, outputs will be displayed separately for each cohort of the trial.

Descriptive statistics for continuous variables will generally contain N (number of patients in that patient set with non-missing values), Mean, Standard Deviation, Minimum (Min), Q1 (25th percentile), Median, Q3 (75th percentile), Maximum (Max). In general, means, standard deviations, medians, Q1 and Q3 will be presented to one more decimal place than the raw data. Minima and maxima will be presented to the same number of decimal places as the raw data.

For time-to-event analysis tables, the set of statistics is: number of patients [N (%)], Number of patients with event [N (%)], Number of patients censored [N (%)], <Time to event> [months] followed by P25 (25th percentile), Median, P75 (75th percentile). If not specified otherwise, the duration as well as time to event will be displayed in months.

Tabulations of frequencies for categorical data will include all possible categories and will display the number of observations in a category as well as the percentage (%) relative to the respective treatment group total. Percentages will be rounded to one decimal place.

In general a category “missing” will be displayed, if there are missing data for the corresponding variable. Percentages will also generally be based on all patients in the respective patient set whether they have non-missing values or not.

Sort order for general categorical variables: If categories correspond to the collected categories on the eCRF and the table shells do not explicitly specify the ordering, the “default ordering” defined by the eCRF is to be used in such cases. If categories are derived the ordering as specified in the table shell document should be used; in general ordinal data (e.g. categorised continuous data) are to be displayed in ascending order.

The denominator of the main categories is defined by the number of patients in the used patient set. The main categories define the denominators of the subcategories. Subcategories should be indented and “[N (%)]” to be displayed only for the main category.

If a table includes only categorical data, “[N (%)]” is to be displayed in the column header.

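### The objective response rate in non-visceral cohorts D2 and F is taken over all treated patients, so it falls as the share of bone-only patients, who cannot have a partial response, rises

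*SAP*

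**What the plan says.** **Endpoint.** OR is a secondary endpoint in D1, D2 and F (protocol 5.1.2). SAP 7.5.2.2 states: "OR as assessed by investigators is defined as a best overall response of CR or PR and will be analysed".

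**Denominator.** The same SAP section announces "Descriptive statistics including number of treated patients, number of patients with" objective response, with the corresponding percentages. SAP 6.3 says "The TS will be used for all planned safety and efficacy analyses", and protocol 7.3 names the same set for the expansion endpoints. SAP section 7 adds: "Percentages will also generally be based on all patients in the respective patient set whether they have non-missing values or not".

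**Who can respond.** SAP 5.1.2 lists "Partial response (PR) – possible only for patients with measurable disease at baseline". Protocol Appendix 10.4 agrees: its time-point table for non-measurable disease has CR, Non-CR/Non-PD, NE and PD, and no PR.

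**Who is enrolled.** For D1, D2 and F, criterion 10 in protocol 3.3.2 reads "Have either measurable disease or non-measurable bone only disease". Criterion 12 requires a visceral metastasis in D1 and none in D2. Criterion 14 requires none in F and names bone among the allowed sites.

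**The concern.** Cohort E, where OR is primary, requires measurable disease (protocol 3.3.2, cohort E criterion 9), so every patient can in principle reach CR or PR. SAP 5.2.2.2 carries the same OR definition to F, D1 and D2. In D2 and F that condition does not hold. A bone-only patient there enters the denominator but can enter the numerator only through CR.

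The three cohorts are not touched equally. A D1 patient has a visceral metastasis and so is not bone-only; under criterion 10 she must then have measurable disease. The bone-only share in D1 is zero by eligibility. In D2 and F it can be anything.

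Visceral status is the axis on which these cohorts were built: protocol 1.2 reports a favourable subgroup signal in patients without visceral metastasis, and protocol 3.1 restricts F to non-visceral disease on that basis. Readers will set the D1 and D2 response rates side by side. A lower rate in D2 could then reflect who was enrolled rather than how active the triplet is.

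**Working it through.** **No plan figure to reproduce.** Protocol 7.7 gives an OR calculation for cohort E only. For D1 and D2 it works with the 18-month PFS rate, and for F with disease control. No ORR assumption and no bone-only share is stated for D2 or F, so the sizes below rest on assumed ranges.

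**Inputs**
- Cohort sizes: D1 30, D2 30, F 20 (protocol synopsis).
- *b*, the bone-only share: zero in D1 by eligibility; assumed 0 to 50% in D2 and F.
- *R*, the ORR in measurable disease: 19.7% is the only breast cancer ORR in the documents (abemaciclib monotherapy, confirmed responses, protocol 1.2). 35% and 50% are assumed.
- *c*, the CR rate in bone-only patients: assumed 0, then 5%.

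**Formulas**
- Treated-set ORR = (1 − *b*) × *R* + *b* × *c*
- Shortfall against measurable disease = *b* × (*R* − *c*)

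The shortfall is zero only if there are no bone-only patients or if they reach CR as often as measurable patients respond.

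**Treated-set ORR with *c* = 0**

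| *R* | *b* = 0% | 10% | 20% | 30% | 40% | 50% |
|---|---|---|---|---|---|---|
| 19.7% | 19.7% | 17.7% | 15.8% | 13.8% | 11.8% | 9.9% |
| 35% | 35% | 31.5% | 28% | 24.5% | 21% | 17.5% |
| 50% | 50% | 45% | 40% | 35% | 30% | 25% |

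D1 stays in the *b* = 0 column throughout.

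**Shortfall at *b* = 30%**
- *c* = 0: 0.30 × 19.7 = 5.9 points; 0.30 × 35 = 10.5 points; 0.30 × 50 = 15 points.
- *c* = 5%: 0.30 × 14.7 = 4.4 points; 0.30 × 30 = 9.0 points; 0.30 × 45 = 13.5 points.

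**In patients.** At *b* = 30%, D2 has 21 measurable patients of 30 and F has 14 of 20. Seven responders in D2 would be 7/30 = 23% of treated patients but 7/21 = 33% of those with measurable disease (exact 95% CI 15% to 57%).

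**Against sampling noise.** The standard error of a difference between two cohorts of 30 is √[p₁(1 − p₁)/30 + p₂(1 − p₂)/30].
- 19.7% v 13.8%: √(0.00527 + 0.00397) = 9.6 points, so the 5.9-point shortfall is about 0.6 standard errors.
- 50% v 35%: √(0.00833 + 0.00758) = 12.6 points, so the 15-point shortfall is about 1.2 standard errors.

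**The case against.** **No contrast is planned.** Protocol 7.2 calls the analyses descriptive and exploratory without formal tests, and 7.3 analyses each expansion cohort separately. Protocol 7.7 gives D1 and D2 different reference 18-month PFS rates (43% and 52%) and assumed rates (60% and 69%), so each cohort is judged on its own scale. This stands. The point concerns how a descriptive rate will be read, and no error rate is affected.

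**The effect may be lost in noise.** At the low end it is below one standard error. This also stands, but the dilution always acts in one direction when bone-only patients reach CR less often than measurable patients respond, and it can be removed with data the derivation needs anyway.

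**Some of it will be visible.** Non-CR/Non-PD is a separate best-response category reserved for non-measurable disease, and SAP section 7 tabulates all possible categories. A reader could count many bone-only patients that way. Those with CR, PD or NE would stay hidden, so the correct denominator could not be recovered.

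**The analysis may already be planned.** A reader might infer that the SAP has no rate in measurable disease at all. The documents do not support so flat a statement. Sections 6.4 and 7.6 are not visible, the contents list shows a redacted entry between 7.5.2.2 and 7.7, and SAP 6.3 refers to a separate technical SAP. What can be said is that the visible text contains no such analysis and no such patient set.

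**Conclusion.** The point holds for D2 and F. In the visible SAP text, their ORR depends on the bone-only share as well as on activity. At an assumed 30% share with no CR in bone-only patients, it sits about 6, 10.5 or 15 points below the rate in measurable disease for an ORR of 19.7%, 35% or 50%. With 5% CR in bone-only patients the shortfall is 4.4, 9.0 or 13.5 points. The true share is unknown, so the true size is too.

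Two stronger readings are tempting and not supported:
- *That D1 is diluted as well*, since criterion 10 is worded for all three cohorts. Criterion 12 removes bone-only patients from D1. It serves only as the undiluted comparator.
- *That the visceral versus non-visceral question is undermined.* The primary endpoint in D1 and D2 is 18-month PFS, which does not use PR. The protocol's disease control definition for F (5.1.1) counts Non-CR/Non-PD lasting at least 24 weeks, so a bone-only patient can succeed without a PR. Only a secondary descriptive endpoint is involved.

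This is a minor improvement to interpretability.

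**What to change.** Unless the redacted SAP text already provides it, keep the treated-set ORR and add for D2 and F:
- the number of patients with measurable and with bone-only disease at baseline;
- the ORR with exact 95% CI among patients with measurable disease at baseline.

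No extra table is needed for D1, where the two denominators coincide apart from eligibility deviations. A footnote should say that D1 has no bone-only patients by eligibility, so its treated-set rate is the one to set beside the measurable-disease rates in D2 and F.

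The best-response categories in SAP 5.1.2 already depend on baseline measurability, so no new definition is required. The baseline list in protocol 5.6 does not name the item, so confirm that it is available in the database.

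The cost is one extra table and smaller denominators (21 instead of 30 in D2 and 14 instead of 20 in F, at the assumed 30% share), with correspondingly wider intervals. Trial conduct does not change.

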7.7 EXTENT OF EXPOSURE

The variables defined in [Section 5.4.2](#) will be summarised descriptively for each dose cohort.

Appropriate summaries of exposure before and from the start of the COVID-19 disruption will also be produced.

7.8 SAFETY ANALYSES

All safety analyses will be performed on the TS (unless otherwise specified; for example, the MTD Set will be used for some safety outputs). Patients in the dose finding cohorts who were replaced within or before the first treatment cycle will be excluded from the determination of the MTD.

7.8.1 Adverse events

The analyses of AEs will be descriptive in nature. All analyses will be based on the number of patients with AEs (not the number of AEs).

For analysis multiple AE occurrence data on the CRF will be collapsed into an AE event provided that all of the following applies:

- All AE attributes are identical (Lowest Level Term (LLT), Common Terminology Criteria for Adverse Events (CTCAE) grade, action taken with trial medication, therapy required, seriousness, reason for seriousness, relationship, outcome, AE of special interest)
- The occurrences were time-overlapping or time-adjacent (time-adjacency of 2 occurrences is given if the second occurrence started on the same day or on the day after the end of the first occurrence)

For further details on summarisation of AE data, please refer to [\(5\)](#) and [\(6\)](#).

Adverse events will be coded with the most recent version of MedDRA. The severity of AEs will be scaled according to CTCAE (CTCAE version 4.03 [\(11\)](#)).

The analyses of adverse events will be based on the concept of treatment-emergent adverse events. That means that all adverse events with an onset between first treatment administration until end of the REP will be assigned as 'on treatment'. All adverse events occurring before first drug intake will be assigned to 'screening' and all adverse events occurring after the residual effect period will be assigned to 'post-treatment'; these AEs will be displayed in listings only. First drug intake includes the run-in period for Cohort E and F. Adverse events will be displayed by the initial dose of study medication administered on the first day of treatment .

An overall summary of adverse events will be presented. The frequency of patients with adverse events will be summarised by treatment, primary system organ class and preferred term. Similar summaries will be produced for the BIcMQ SARS-COV-2-infections.

Proprietary confidential information © 2021 Boehringer Ingelheim International GmbH or one or more of its affiliated companies

Separate tables will be provided for patients with drug-related adverse events, adverse events leading to dose reduction, adverse events leading to discontinuation, serious adverse events, serious drug-related serious adverse events, adverse events leading to death, other significant adverse events, adverse events of special interest, and adverse events fulfilling the DLT definition.

Sorting order:

In tables presenting System Organ Classes (SOCs) and Preferred Terms (PTs), SOCs will be sorted alphabetically and PTs (within SOC) by descending frequency.

Reporting of CTCAE grades in tables:

In tables showing AEs by worst CTCAE grade, AEs with missing CTCAE grade will only be displayed under the category "All grades", but no category "Missing grade" will be displayed. Therefore the categories "Grade 1" to "Grade 5" might not add up to the category "All grades"; a footnote will explain this handling.

Displaying of CTCAE grades in AE tables (Section 15) will be "All grades", "Grade 1", "Grade 2", "Grade 3", "Grade 4", and "Grade 5" separately. In the appendix (Section 16.1.13.1, the categorisation "All grades", "Grade 1/2", "Grade 3/4/5", will be used.

Listings of adverse events

Adverse events will be reported with start and end day as calculated from the first day of treatment with study medication. This includes the run-in period for the Cohort E and F.

Incidence and severity of adverse events

The incidence of AEs overall (irrespective of relatedness to study medication), related AEs, and serious AEs (SAE) will be reported by severity according to CTCAE grades.

Other significant adverse events

Other significant AEs are defined as serious and non-serious AEs that lead to dose reduction or permanent discontinuation of study medication. Their incidence will be reported by severity according to CTCAE grades.

A listing of patients who developed 'other significant' AEs will be provided and a flag for serious and non-serious will be included.

AEs leading to dose reduction or permanent discontinuation will include:

- AEs leading to dose reduction of xentuzumab
- AEs leading to dose reduction of abemaciclib
- AEs leading to permanent discontinuation of xentuzumab
- AEs leading to permanent discontinuation of abemaciclib

AEs leading to death

AEs leading to death during the on-treatment period will be tabulated in a separate table. In this table no CTCAE grades will be shown. For fatal AEs without CTCAE grade 5 or missing

Proprietary confidential information © 2021 Boehringer Ingelheim International GmbH or one or more of its affiliated companies

grade, the grade will be imputed as CTCAE grade 5. Reported fatal AEs that occurred in the post-treatment period will be listed within the listing containing all post-treatment AEs.

Protocol-specified Adverse Events of Special Interest (AESI)

Protocol-specified AESIs are specified in the CTP Section 5.3.6.1. Their incidence will also be reported. DLTs are considered as AESIs only in the dose finding cohorts.

Adverse events by user defined AE categories (UDAEC)

User defined adverse events categories (UDAEC) as defined on project level by the pharmacovigilance working group will be derived and the latest version will be used for the analysis. Details of the current version are presented below in the table below.

Table 7.8.1: 1 Adverse events by user defined AE categories

SSC	Group[#]
Hepatic impairment	Drug related hepatic disorders – comprehensive search (SMQ)
Hyperglycaemia narrow	Hyperglycaemia/new onset diabetes mellitus (SMQ) - narrow
Infusion related reaction	Hypersensitivity (SMQ) - broad
Non-infectious pneumonitis	Interstitial lung disease (SMQ) - narrow
Renal insufficiency	Acute renal failure (SMQ) - broad and narrow; Proteinuria (SMQ)-broad and narrow; Glomerulonephritis and nephrotic syndrome:HLT
Weight loss	Weight loss (BIcMQ) – broad and narrow
Neutropenia	Haematopoietic leukopenia (SMQ) – narrow
Stomatitis	Stomatitis (BIcMQ) – broad and narrow
Asthenia	MedDRA PTs: Asthenia, Fatigue, Lethargy, Malaise, and Decreased activity
Haemorrhage	Haemorrhage laboratory terms (SMQ)-narrow; Haemorrhage terms (excl laboratory terms) (SMQ)-broad and narrow
Anemia	Haematopoietic erythropenia (SMQ) – broad and narrow
Thrombocytopenia	Haematopoietic thrombocytopenia (SMQ) - narrow
Thromboembolism	Embolic and thrombotic events, vessel type unspecified and mixed arterial and venous (SMQ)-broad and narrow
Bradycardia	Torsade de pointes/QT prolongation (SMQ), PT of Bradycardia
Rash	BIcMQ: Skin eruptions (subsearch2: Skin rash potentially related to drug use [broad and narrow])

[#] This column indicates whether the Term(s) provided in the first column are MedDRA preferred terms (**PT**), Standardised MedDRA Queries (**SMQ**) or BI customised MedDRA Queries (**BIcMQ**).

The incidence of AE by UDAEC will be analysed.

Proprietary confidential information © 2021 Boehringer Ingelheim International GmbH or one or more of its affiliated companies

